Analyses. *Inferential Paradigm and Bayesian Analyses.* Following recommendations in the clinical trial literature analyses we will proceed using parallel frequentist and Bayesian statistical inference (30, 31). The Bayesian inferential paradigm can provide probabilistic estimates of effects irrespective of sample size. Bayesian analyses will focus on posterior probabilities ≥ 0.75 (equivalent to a Bayes factor = 0.33 or 3.0) that parameter estimates are greater or less than zero to emphasize the value in discerning treatment effects in a small trial. Power calculations for the frequentist analyses are derived using G*Power v. 3.1.9.2 and focus on the residual change model described in Hypothesis 2a. As noted, the Bayesian analyses will provide the primary inferential results; sample size considerations for the frequentist analyses are limited by the small sample size and provided as due diligence. Given alpha = 0.05, a sample size $N = 40$ provides 80% power to detect a Cohen's $f = 0.45$. Frequentist analyses will provide conventional interpretation of the relationships between predictors and outcomes: the probability of the data, given the null hypothesis. Bayesian analyses will incrementally update specified prior information regarding effects to directly yield the probability of an alternative hypothesis. Bayesian analyses will employ informative priors as they develop in the literature; otherwise, weakly informative priors will be used as a default (e.g., for regression coefficients: $\sim N[\mu=0, \sigma^2=100]$; for non-linear outcome variables this prior applies to the coefficient within the link-function). Sensitivity analyses using optimistic and pessimistic, skeptical priors will evaluate prior assumptions. Assessing the convergence of Bayesian analyses on the posterior distributions via Monte-Carlo Markov chain (MCMC) will use diagnostic evidence including effective sample size and scale reduction factors. Evaluation of posterior distributions will permit statements regarding the probability that effects of varying magnitudes exist, given the data, even with a small sample size. *Descriptive statistics* will evaluate measures of central tendency and frequencies for all continuous and categorical variables (respectively) measured in the study. Correlation analyses (i.e., Pearson's r , Spearman's ρ) will be used to evaluate broad patterns of relationships across variables. Preliminary data analyses will inspect relationships between sample characteristics (e.g., demographics), experimental group (e.g., active vs.

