Inclusion criteria will be: (1) diagnosis of possible or probable ADRD according to the National Institute of Aging – Alzheimer’s Association diagnostic criteria (34); (2) mild or moderate dementia, **as defined by a MMSE score between 14 and 26** (35, 36); (3) clinically meaningful apathy for at least four weeks, clinically diagnosed according to 2018 Apathy Diagnostic Criteria (37) or defined as Neuropsychiatric Inventory (**NPI-Q**) apathy score equal or above 4 (i.e., severity of ‘moderate’ or greater **and caregiver distress ‘mild or greater’** (38-40); (4) stable doses of cholinesterase inhibitors, memantine and other psychotropic medications for at least three months.

Exclusion criteria will be: (1) unstable medical conditions; (2) history of epilepsy; (3) metallic objects in the brain; (4) diagnosis of major depression and/or a score higher than 18 on the Cornell Scale for Depression in Dementia (41).

Recruitment and Retention. Subjects will be recruited at the *UTHealth Geriatric Neuropsychiatry Clinic, the Harris County Psychiatric Center (HCPC)* ([name]) and the *UT Physicians Center for Healthy Aging* ([name]). As serious adverse effects and problems with the device use are not anticipated, it is expected a high retention rate. The remote supervision of the tDCS or tDCS sham daily sessions by trained research staff will contribute to the retention of subjects during the trial.

Training plan. Patients will be instructed on treatment at baseline, when they will receive the device. A trained research staff will instruct the participant's caregiver on how to handle the equipment. All sessions will be remotely supervised by trained research (RA) staff, who will be able to answer questions during the sessions and verify that the device is being used correctly.

Study Procedures

Feasibility measures will include recruitment rate (per month), randomization success, blind success, retention and attrition rates. Overall consent and completion rates will be evaluated via descriptive statistics. Generalized linear modeling (GLM) will evaluate treatment group differences in consent and completion rates. We expect that a high proportion of participants will consent to participate (> 80%) and complete the study (> 70%).

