Acceptability will be evaluated using the method proposed by Ahn et al. (2019) (29). Participants and/or their caretakers will be asked to apply a Likert scale (from 0 [strongly disagree] to 10 [strongly agree]) to answer ten affirmatives regarding the use of home-based tDCS. For example, question 1: "It was easy to prepare the device and accessories", question 7: "I felt confident using the device." Overall acceptability across groups will be evaluated by descriptive measures of satisfaction ratings. GLM will model participant satisfaction ratings as a function of treatment group (active vs. sham tDCS). We expect that participant satisfaction ratings at the end of treatment will demonstrate high acceptance of tDCS treatment in the present sample.

Safety will be assessed with a questionnaire about side effects that include itching, burning, headache, fatigue, and dizziness (29). Descriptive statistics will describe raw frequencies of AEs and side effects. Treatment group differences in AEs and side effects will be evaluated via Chi-square and Fisher's exact test of contingency tables. We expect that adverse events and side effects will be rare, and any that may occur will be mild.

The primary clinical outcome measure will be change on the Apathy Evaluation Scale score (42), the best-validated scale for measuring apathy in AD, which consists of 18 items phrased as questions that are to be answered by the caregiver on a four-point Likert scale, with higher scores indicating greater severity of apathy. Apathy will be

assessed at baseline, during treatment (weeks 2, 4 and 6) and 6 weeks post-treatment. Our hypothesis is that active tDCS group will demonstrate lower apathy scores at the end of treatment relative to sham tDCS. GLM will evaluate residual change by modeling apathy at the end of treatment as a function of treatment group, controlling for apathy at the beginning of treatment. This analysis is a regression-based analogue to ANCOVA that permits non-normally distributed outcome distributions. Follow-up analyses will evaluate change over time across groups via GLM with multilevel components (GLMM) as well as cross-sectional analyses within each measurement time point via GLM.

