Inferential Paradigm and Bayesian Analyses. Following recommendations in the clinical trial literature analyses we will proceed using parallel frequentist and Bayesian statistical inference (30, 31). The Bayesian inferential paradigm can provide probabilistic estimates of effects irrespective of sample size. Bayesian analyses will focus on posterior probabilities ≥ 0.75 (equivalent to a Bayes factor = 0.33 or 3.0) that parameter estimates are greater or less than zero to emphasize the value in discerning treatment effects in a small trial. Power calculations for the frequentist analyses are derived using G*Power v. 3.1.9.2 and focus on the residual change model described in Hypothesis 2a. As noted, the Bayesian analyses will provide the primary inferential results; sample size considerations for the frequentist analyses are limited by the small sample size and provided as due diligence. Given alpha = 0.05, a sample size N = 40 provides 80% power to detect a Cohen's $f = 0.45$. Frequentist analyses will provide conventional interpretation of the relationships between predictors and outcomes: the probability of the data, given the null hypothesis. Bayesian analyses will incrementally update specified prior information regarding effects to directly yield the probability of an alternative hypothesis. Bayesian analyses will employ informative priors as they develop in the literature; otherwise, weakly informative priors will be used as a default (e.g., for regression coefficients: $\sim N[\mu=0, \sigma^2=100]$; for non-linear outcome variables this prior applies to the coefficient within the link-function). Sensitivity analyses using optimistic and pessimistic, skeptical priors will evaluate prior assumptions. Assessing the convergence of Bayesian analyses on the posterior distributions via Monte-Carlo Markov chain (MCMC) will use diagnostic evidence including effective sample size and scale reduction factors.

Evaluation of posterior distributions will permit statements regarding the probability that effects of varying magnitudes exist, given the data, even with a small sample size.

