Descriptive statistics will evaluate measures of central tendency and frequencies for all continuous and categorical variables (respectively) measured in the study. Correlation analyses (i.e., Pearson's r , Spearman's ρ) will be used to evaluate broad patterns of relationships across variables. Preliminary data analyses will inspect relationships between sample characteristics (e.g., demographics), experimental group (e.g., active vs. sham tDCS), and specified outcome variables (e.g., Apathy) via traditional statistical tests (e.g., chi-square; Mann-Whitney; t -tests). Any sample characteristic variables that demonstrate a relationship with both predictor and outcome variables in a given model meet criteria for being a potential confounder (32, 33) and will be included as a covariate in such models for hypothesis testing.

Statistical modeling will primarily use generalized linear modeling (GLM) with multilevel components (GLMM) for correlated observations. Potentially nonlinear relationships between predictors and outcomes will be evaluated via inclusion of polynomial or spline effects. Continuous, dichotomous, and count-distributed data will utilize linear, logistic, and Poisson/negative binomial regression, respectively (each with a canonical link function). Evaluation of distributional assumptions will use residual plots, formal statistical tests, and posterior predictive checking. Violations of assumptions will be addressed via transformation, robust estimation, stratification, and/or coefficient scaling where appropriate. Statistical analyses will be performed using the R statistical computing environment via packages lme, rstan, and brms.

Missing data will be addressed via maximum likelihood, explicit modeling of missingness, or imputation where appropriate. Each approach is robust to ignorable missingness (i.e. MCAR and MAR). Sensitivity analyses will permit evaluation of the robustness of findings to missing data assumptions. While Bayesian analyses are not influenced by traditional concerns of multiplicity, for the frequentist analyses, all primary outcome variables (those specified by name in the hypothesis statements) will be evaluated at the $\alpha = 0.05$ statistical significance level, while any secondary or otherwise post hoc analyses will employ false discovery rate (FDR) to control for Type I error.

Ethics/Protection of Patient Confidentiality

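### The stated 80% power at f = 0.45 needs a week-6 apathy score from all 40 randomised participants; no figure allows for loss, although study completion is put only at a floor of 70%

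*Combined protocol and SAP*

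**What the plan says.** The power statement appears twice in identical substance, under Study Design (Analyses) and under Statistics. At alpha 0.05, "a sample size N = 40 provides 80% power to detect a Cohen's" f of 0.45. The text ties it to the residual-change model. Study Procedures describes that model for the primary clinical outcome: "GLM will evaluate residual change by modeling apathy at the end of treatment as a function of treatment group", with adjustment for apathy at the start of treatment. Treatment ends at week 6, and Table 1 schedules the AES at baseline and at weeks 2, 4, 6 and 12.

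Study Design and Study Population give 40 as the number randomised, 20 per arm. Study Population says this number came from achievable recruitment and available funding. No section inflates it for dropout or restates power for a smaller number.

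On attrition, Study Procedures says: "We expect that a high proportion of participants will consent to participate (> 80%) and complete the study (> 70" (both figures are percentages). Recruitment and Retention adds, without a number, that "it is expected a high retention rate". On missing values: "Missing data will be addressed via maximum likelihood, explicit modeling of missingness, or imputation where appropriate". On the weight of the power figure: "sample size considerations for the frequentist analyses are limited by the small sample size and provided as due diligence". The Bayesian analyses supply the primary inference.

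**The concern.** The plan anticipates some attrition in one place and assumes none in another. Because 40 is both the number randomised and the number in the power statement, the statement is right only if nobody lacks a week-6 AES. There is also no slack: with all 40 scores, power is already slightly under 80%.

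What is at stake is how a frequentist result will be read. A reader will take f = 0.45 as the effect this trial can detect with 80% power. If some week-6 scores are lost, the detectable effect is larger, and a non-significant AES comparison could be given more weight against an effect of that size than it deserves. The Publication Plan says the results will inform adjustment or expansion of the protocol, so an accurate statement of what the trial could detect has some practical use.

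**Working it through.** **Inputs**
- Alpha 0.05, N = 40, f = 0.45 and stated power 80%: power statement, Statistics and Study Design.
- Model: week-6 AES on arm with one covariate, baseline AES: Study Procedures. The power statement points to a Hypothesis 2a; no hypothesis carries that label, and I take it to be this AES model.
- Allocation 1:1, 40 randomised: Study Design, Study Population.
- Study completion above 70%: Study Procedures.
- Sidedness is not stated. I assume the non-directional F test, which is two-sided for two groups.

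**Formula**
The test statistic is F with 1 and N − 3 degrees of freedom (two groups, one covariate). Under the alternative it is noncentral F with λ = f²N. Power = P(F′ > F at the 95th percentile). N is the number with a week-6 AES, with equal arms assumed.

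**The plan's own figure**
λ = 0.45² × 40 = 0.2025 × 40 = 8.10; df = 1 and 37; critical F = 4.105. Power = 79.15%.

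Without the covariate it is 79.2%, and the normal approximation gives 81.2%. All are within two points of the stated 80%. A one-sided test gives 87.5% and does not match, which supports the two-sided assumption. The plan's figure is therefore reproduced, and it uses all 40 randomised as analysed. At f = 0.45, 41 scores are needed to reach 80%.

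**How low could the count go?**
0.70 × 40 = 28, so the smallest whole number above 70% of those randomised is 29.

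**Power with fewer week-6 scores (complete-case)**

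| Week-6 scores | λ = 0.2025 N | Denominator df | Power at f = 0.45 | f detectable with 80% power |
|---|---|---|---|---|
| 40 | 8.10 | 37 | 79.15% | 0.455 |
| 38 | 7.70 | 35 | 76.95% | 0.467 |
| 36 | 7.29 | 33 | 74.56% | 0.481 |
| 32 | 6.48 | 29 | 69.17% | 0.512 |
| 29 | 5.87 | 26 | 64.55% | 0.541 |

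A 15/14 split at 29 scores gives 64.5%, so the equal-arms assumption matters little there. Clearly uneven loss would cost more: an 18/11 split gives about 62%.

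**The case against.** **The sentence is true as written.** It is conditional on N = 40 and is reproduced. This stands: the defect is a missing figure for fewer scores, not a wrong calculation.

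**65% is what the plan predicts.** A reader might infer this from the completion figure. The documents do not support it. More than 70% is a floor, which the plan calls a high proportion, and retention is separately expected to be high. The General Information table gives a 12-week study period, so completing the study most naturally means reaching week 12. The power model needs only week 6, and a participant lost between the two visits costs it nothing. The AES also has "18 items phrased as questions that are to be answered by the caregiver on a four-point Likert scale", so stopping stimulation need not lose the score. Twenty-nine is a lower-bound illustration.

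**A specific intermediate count can be derived.** A reader might divide the completion figure by the consent figure (70/80 = 87.5%, or 35 of 40). Both are lower bounds, and a ratio of two lower bounds bounds nothing. The plan does not say that they share a denominator either. No particular count follows from these figures.

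**Complete-case analysis is not the plan.** This is correct. Maximum likelihood or imputation could draw on AES at weeks 2 and 4. The recovery depends on correlations between visits and on who has the earlier scores, neither of which the documents give. The plan's claim that these methods are robust to ignorable missingness concerns bias, not retained power. They cannot be shown to restore 80%, since even full data give 79%.

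**Little depends on the figure.** This also stands. Efficacy is the secondary goal, retention and attrition are themselves feasibility outcomes, the Bayesian results are primary, and N was not derived from power. A reader might still conclude that the trial should be enlarged; the documents give no basis for that.

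**Conclusion.** The concern holds as a minor reporting correction. The stated 80% at f = 0.45 is about 79% and applies only if all 40 randomised participants provide a week-6 AES. Any loss takes complete-case power below that: 2 scores lost, about 77%; 4 lost, about 75%; 8 lost, about 69%; and about 65% at the 29-score illustration, where 80% power needs f of about 0.54.

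This rests on a two-sided test, one baseline covariate, roughly equal loss by arm and complete-case analysis. Power under the planned missing-data methods may be higher than these figures, by an unknown amount. Nothing here shows a calculation error, an inadequate sample size or a forecast of 30% dropout.

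**What to change.** Replace the power sentence in both places (Study Design, Analyses; and Statistics) with wording such as:

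> Given alpha = 0.05 (two-sided), power at f = 0.45 is about 79% if all 40 participants provide a week-6 AES, about 75% with 36, and about 65% with 29 as a lower-bound illustration. These are complete-case figures; 80% power then requires f of about 0.455, 0.48 and 0.54 respectively. The planned likelihood or imputation methods may recover part of the loss.

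The cost is one reworded sentence in two places. N, visits, data collection and analysis are unchanged. The only downside is a less favourable stated figure.
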